2.1 Study Rationale

Most prostate cancer at diagnosis (in Europe and the USA) is localized disease. The majority of patients receive local treatment alone or with adjuvant androgen deprivation therapy (ADT). Many patients will eventually become resistant to ADT and develop castration-resistant prostate cancer (CRPC) ([Dai et al. 2017](#)). Contemporary research has led to the development of multiple active treatments for men with advanced disease, in addition to ADT. Management of CRPC involves the sequential use of these approaches, with the goals of prolonging survival and minimizing complications, but there is also a need to maintain quality of life.

There are multiple androgen receptor (AR) inhibitors indicated for prostate cancer with proven efficacy. However, these drugs are associated with adverse events including fatigue, cognitive dysfunctions, anorexia, sarcopenia, muscle weakness, and falls. There is an unmet medical need to improve patients' daily function, quality of life, and safety with an AR inhibitor with a better safety profile. Enzalutamide is the most frequently used AR inhibitor indicated for the treatment of patients with CRPC.

The Phase 3 ARAMIS study of AR inhibitor darolutamide showed clinically and statistically significant prolongation of time to metastasis in patients with non-metastatic CRPC treated with darolutamide as compared to placebo ([Fizazi et al. 2019](#)). The study also showed that darolutamide was well tolerated and has a differentiated safety profile from enzalutamide, which is why darolutamide-treated patients may have improved function for activities of daily living, less fatigue, and improved cognition. However, currently there has not been a study to assess physical function and daily activities in patients treated with darolutamide.

The primary aim of this study is to evaluate the effects of treatment with darolutamide or enzalutamide on physical function as demonstrated by changes in balance, mobility, and cognitive function in participants with CRPC. Standardized assessments of physical function including the Timed Up and Go (TUG) and Short Physical Performance Battery (SPPB) will be used to monitor participants' physical function on treatment ([Belch et al. 2003](#)). Each participant will also use an accelerometry device to track daily physical activity.

The cognitive function assessments included in this study are the Hopkins Verbal Learning Test, Revised (HVLN-R), Trail Making Test (TMT), Controlled Oral Word Association Test (COWA), and Functional Assessment of Cancer Therapy-Cognitive (FACT-Cog). Fatigue and depression will be assessed using the Brief Fatigue Inventory (BFI) and Patient Health Questionnaire-9 (PHQ-9), respectively.

2.2 Background

Darolutamide (ODM-201/BAY 1841788) is a novel non-steroidal AR inhibitor that appears to negligibly cross the blood-brain barrier, reducing the occurrence of central side effects including seizures. Darolutamide has been found to block the activity of all tested/well-known mutant ARs in prostate cancer, including the recently identified clinically-relevant F876L

mutation that produces resistance to enzalutamide and apalutamide, and shows a higher binding affinity (9 nM) to AR compared with known second-generation antiandrogens and greater inhibitory efficacy ([Eikelboom et al. 2017](#)).

Darolutamide has been investigated in multiple Phase 1, 2, and 3 trials. Detailed information can be found in the Investigator's Brochure (IB).

The Phase 1/2 ARADES study in patients with metastatic CRPC showed tolerability of darolutamide in the population with advanced prostate cancer with metastatic lesions. The Phase 1 component of ARADES was an open-label, uncontrolled, non-randomized, multicenter, dose-escalation safety study with single- and multiple-dose pharmacokinetic (PK) evaluation in 24 patients. No dose-limiting toxic effects were reported and the maximum tolerated dose was not reached ([Derry and Loke 2000](#)).

The Phase 2 part of the trial randomized 124 patients to one of three darolutamide doses, with a primary endpoint of proportion of patients with PSA response ($\geq 50\%$ decrease in serum PSA) at Week 12. PSA response was achieved by 11 patients (29%) in the 200 mg group, 13 (33%) in the 400 mg group, and 11 (33%) in the 1400 mg group. The most common treatment-emergent adverse events (TEAEs) were fatigue or asthenia (12% of patients), hot flush (5%), and decreased appetite (4%) ([Derry and Loke 2000](#)).

The multinational, randomized, double-blind, placebo-controlled, Phase 3, efficacy and safety study of darolutamide in men with high-risk non-metastatic castration-resistant prostate cancer (ARAMIS) met the primary endpoint of metastasis-free survival (MFS). In total, 1509 patients underwent randomization (955 to the darolutamide arm and 554 to the placebo arm). The median MFS was 40.4 months with darolutamide, as compared with 18.4 months with placebo (hazard ratio for metastasis or death in the darolutamide arm, 0.41; 95% confidence interval, 0.34 to 0.50; $p < 0.001$). Darolutamide was also associated with benefits with regard to all secondary endpoints, including overall survival, time to pain progression, time to cytotoxic chemotherapy, and time to a symptomatic skeletal event.

Darolutamide treatment was well-tolerated with comparable incidence of the most common TEAEs and similar incidence of permanent discontinuations of treatment between the darolutamide and the placebo arms. Incidences of TEAEs were below 10% in both treatment arms, with the exception of fatigue (12.1% darolutamide vs. 8.7% placebo) ([Fizazi et al. 2019](#)).

The median MFS with darolutamide in ARAMIS is similar to that in two other randomized controlled trials with enzalutamide and apalutamide in patients with non-metastatic CRPC. Median MFS was 36.6 months with enzalutamide (vs. 14.7 with placebo) in the PROSPER Phase 3 trial, and was 40.4 months with apalutamide (vs. 16.2 months with placebo) in the SPARTAN Phase 3 trial ([Hussain et al. 2018](#), [Smith et al. 2018](#)). Rates of fatigue and asthenia, common adverse events for patients receiving hormone-targeted therapy for advanced prostate cancer, were lower in ARAMIS than in PROSPER and SPARTAN. In contrast to apalutamide and enzalutamide, darolutamide was not associated with increased rates of falls or fractures compared with placebo despite few patients using osteoclast-targeted therapies. Seizures were noted as a potential risk in the dose escalation and toxicity studies of enzalutamide ([Scher et al. 2010](#)). The incidence of seizure events was low and similar in the darolutamide and placebo arms; none of the patients with a medical history of seizure (12 in the darolutamide arm) experienced a seizure on study. Rates of rash and hypothyroidism, which were increased in patients receiving apalutamide compared with placebo, were low and similar between the darolutamide and placebo arms. Incidences of hypertension and central nervous system (CNS)-related adverse events were also low and similar between

darolutamide and placebo arms in ARAMIS. In PROSPER and SPARTAN, rates of hypertension and CNS-related adverse effects, such as mental impairment disorders and dizziness, were more common in patients receiving enzalutamide or apalutamide compared with placebo. The similar incidence of seizures, dizziness, and cognitive impairment in the darolutamide and placebo arms of ARAMIS may be linked to darolutamide's low blood–brain barrier penetration observed in preclinical studies ([Zurth et al. 2018](#)).

However, currently there has been no study to assess differences in physical function and the influence on quality of life of CRPC patients treated with these treatment options, and the effect of the treatments on daily function, quality of life, and activities are unknown. This study is designed to assess physical function, daily activity level, cognitive functions, and influence of secondary events in patients with CRPC treated with darolutamide and enzalutamide.

2.3 Benefit/Risk Assessment

The available clinical data suggest that darolutamide use is well-tolerated and safe for patients with non-metastatic CRPC. Darolutamide has been shown to significantly increase the time to metastasis compared to placebo while providing a favorable safety profile with low risk for adverse reactions that could deteriorate patients' quality of life. Therefore, the benefit from darolutamide treatment is significantly greater than the risk imposed by the treatment.

More detailed information about the known and expected benefits and risks and reasonably expected adverse events of darolutamide can be found in the IB. Information about the adverse events of enzalutamide is available in the prescription information of enzalutamide ([XTANDI™ Prescribing information](#)).

3. Objectives and Endpoints

Objectives	Endpoints
Primary	

The primary objective of this study is to compare the effects of treatment with darolutamide vs. enzalutamide on physical function as assessed by the TUG test in participants with castration-resistant prostate cancer.
	
Proportion of participants with a worsening in TUG time during the 24-week period from baseline. Worsening is defined as an increase of at least 1 second in TUG time from baseline. (The MCID in TUG time is 1 second (Davies et al. 2016))

Secondary	

The secondary objectives of this study are to:
 
 • Compare the effects of treatment with darolutamide vs enzalutamide on physical function, as assessed by the TUG test at 12 and 24 weeks, and by 52 weeks. • Compare the effects of treatment with darolutamide vs enzalutamide on physical function as assessed by the SPPB test at 12 and 24 weeks, and by 24 and 52 weeks. • Assess the effects of treatment with darolutamide vs. enzalutamide on daily activity as assessed by accelerometry at 12 and 24 weeks, and by 24 and 52 weeks. • Compare the effects of treatment with darolutamide versus enzalutamide on cognitive function as assessed by HVLT-R, TMT, COWA, and FACT-Cog • Compare the effects of treatment with darolutamide versus enzalutamide on fatigue as assessed by the BFI • Compare the effects of treatment with darolutamide vs. enzalutamide on depression as assessed by the PHQ-9 • Evaluate safety, including AEs of interest, of participants treated with darolutamide vs. enzalutamide 
 • Evaluate the effect of treatment with darolutamide or enzalutamide on PSA, survival status, and exposure 	
Physical Function:
 
 • Proportion of participants with an increase of at least 1 second in TUG time at 12 and 24 weeks and during the 52 weeks from baseline. • Time to worsening (increase of at least 1 second) in TUG time • Proportion of participants with a worsening in SPPB total score at 12 and 24 weeks and during the 24 weeks and 52 weeks from baseline. Worsening is defined as a decline of at least 0.5 points in SPPB total score. 
Daily Activity:
 
 • Mean change from baseline in daily physical activity at 12 and 24 weeks, and during the 24 weeks and 52 weeks from baseline. • Mean change from baseline in accelerometer-assessed proportion of time spent in light to vigorous physical activity based on a threshold of >100 activity counts per minute at 12 and 24 weeks, and during the 24 weeks and 52 weeks from baseline. 
Cognitive Function:
 
 • Proportion of participants with a decline in cognitive function during the 24 weeks and 52 weeks from baseline, as assessed by HVLT-R, TMT, and COWA. See Table 8–1 for the definition of decline for each test. • Proportion of participants with a decline using a selected domain of FACT-Cog. Decline is defined as a decrease of >10 points during the 24 weeks and 52 weeks from baseline. 
Fatigue:
 
 • Proportion of participants with a worsening of fatigue during the 24 weeks and 52 weeks from baseline. Worsening is defined as an increase of at least 1 point in worst level of fatigue from baseline by 24 weeks and 52 weeks (based on item 3 of the BFI). • Proportion of participants with an increase of at least 1 point in fatigue interference by 24 weeks and 52 weeks from baseline (based on items 4A-F of the BFI).

Objectives	Endpoints
	
Depression:
 
 • Proportion of participants with a worsening in scores in the PHQ-9 during the 24 weeks and 52 weeks from baseline. Worsening is defined as an increase of at least 1 point in worst level of depression from baseline by 24 weeks and 52 weeks. 
Safety
 
 • All treatment emergent AEs, SAEs, and AEs leading to discontinuation • AEs of interest, including falls, fractures, and hypothyroidism 
Exposure and other:
 
 • Time to deterioration of KPS defined as at least a 10 point decline from baseline • Treatment exposure of the study intervention including time on treatment • Dose reductions of study intervention • Time to PSA progression (as per PCWG3 criteria) • Survival status

4. Study Design

4.1 Overall Design

This is a randomized, open-label, multicenter, Phase 2b study to be conducted with a total of approximately 150 participants with CRPC who have not previously been treated with apalutamide, darolutamide, or enzalutamide. CRPC patients with a history of treatment with abiraterone may be eligible if they have not progressed and discontinued treatment within 6 months before signing the ICF for this study.

The study consists of two phases, a lead-in phase and a randomized phase (see Figure 1–1). In the lead-in phase, approximately 30 participants will be treated with darolutamide. Following the primary evaluation of the lead-in phase, approximately 120 participants will be randomized in a 1:1 ratio to receive either darolutamide (600 mg twice daily) or enzalutamide (160 mg once daily) in the randomized phase of the study. Randomization will be stratified by age (<75, ≥75 years).

At the end of the lead-in phase of the study, the compliance and variability of the endpoints and overall feasibility of the study execution will be assessed. The randomized phase of the study will start only after the primary evaluation of the lead-in phase. Depending on the results of the evaluation, the primary endpoint for the randomized portion of the study may be changed. The final study design and endpoints for the randomized phase will be determined based on the lead-in cohort of 30 participants. The decision to move to the randomized phase of the study will involve reviewing the findings from the lead-in phase of the study with the members of the steering committee.

The primary evaluation of the lead-in phase will occur when at least 30 participants in the lead-in phase have been on the study for at least 24 weeks, unless the participant discontinued due to lost to follow-up, withdrawal, or death. Additional participants may be enrolled in the lead-in phase if necessary.

The following endpoints will be evaluated at the end of the lead-in phase:

- the proportion of participants with a worsening in TUG time at week 12 and 24 and during the 24-week and 52-week period from baseline. Worsening is defined as an increase of at least 1 second in TUG time from baseline.
- the proportion of participants with a worsening in SPPB total score at week 12 and 24 and during the 24-week and 52-week period from baseline. Worsening is defined as a decline of at least 0.5 points in SPPB total score.
- the proportion of participants with a decline in cognitive function during the 24-week period from baseline, as assessed by HVLT-R and TMT

The suggested sample size for the randomized phase is based on the assessment of TUG test as the primary endpoint; however, after the feasibility assessment, the appropriate endpoint and the time point and time frame of evaluation of the endpoint for this part of the study will be chosen and the sample size will be reassessed.

The study is designed to evaluate physical function, including balance and daily activity, in participants treated with darolutamide or enzalutamide. It will also evaluate, safety, cognitive function, fatigue, and survival in participants treated with darolutamide or enzalutamide.

Participants will receive treatment (darolutamide or enzalutamide) until toxicity or disease progression and receive assessments during treatment. The study will continue until at least 52 weeks after the initial dose of the last participant, unless the participant discontinued due to lost to follow-up, withdrawal, or death. All participants will be followed up for survival status until the end of the study unless participants withdraw their informed consent.

The primary analysis for the lead-in phase will be performed when the last participant in the lead-in phase has been on the study for at least 24 weeks, unless the participant discontinued due to lost to follow-up, withdrawal, or death.

The primary analysis for the randomized phase for the study will occur when last participant in the randomized phase of the study has been on the study for at least 24 weeks, unless the participant discontinued due to lost to follow-up, withdrawal, or death. A final analysis for the randomized phase for the study will occur when last participant in the randomized phase of the study has been on the study for at least 52 weeks, unless the participant discontinued due to lost to follow-up, withdrawal, or death.

No data monitoring committee, dose escalation committee, or similar review group will be used for this study. The study will be conducted only in the USA at approximately 20 sites.

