9.2 Sample Size Determination

Lead-in phase

Approximately 30 participants will receive study intervention in the lead-in phase of the study. The example point estimates of decline rates (physical or cognitive function) and the corresponding 2-sided 95% CI (based on exact binomial distribution) are shown in [Table 9-1](#). For instance, decline/worsening for TUG test is defined as an increase of at least 1 second in TUG time from baseline. The definition of decline in cognitive functions is provided in [Section 9.4.2](#). The values are provided as a reference rather than a basis for decision making.

Table 9–1: Estimated Decline Rates and 2-sided 95% Confidence Intervals

Number of participants with a decline	Observed Decline Rate	95% CI		Width (%)
		Lower limit	Upper Limit	
0	0	0.00	11.57	11.57
6	20%	7.71	38.57	30.85
12	40%	22.66	59.40	36.74
18	60%	40.60	77.34	36.74
24	80%	61.43	92.29	30.85
30	100%	88.43	100.00	11.57

CI: confidence interval

Randomized phase

The sample size calculation for the randomized phase of the study is based on the primary endpoint of physical decline (using TUG test as an example). In the event that the primary endpoint or the assumed rate of decline changes based on results from the lead-in phase of the study, the sample size will be adjusted accordingly.

Approximately 120 participants in the randomized phase of the study will provide 85% power to detect a difference of 20% in the two arms using one-sided alpha of 10%. This is assuming that 20% of participants in the darolutamide arm and 40% of participants in the enzalutamide arm will have a worsening in physical function at 24 weeks as measured by the TUG test. Worsening is defined as an increase of at least 1 second in TUG time from baseline. A 10% drop-out rate is assumed.

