## **5.4 Efficacy Analyses**

The primary analysis for the lead-in phase of the study will occur when the last participant has been on the study for at least 24 weeks, unless the

participant discontinued due to being lost to follow-up, withdrawal, or death.

The final analysis for the randomized phase of the study will occur when the last participant has been on the study for at least 52 weeks after the start of study intervention, unless the participant discontinued due to being lost to follow-up, withdrawal, or death.

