## **5.5.2 Secondary Endpoints Analyses**

### **Physical function**

- Proportion of participants with a worsening in TUG time from baseline at 12 and 24 week study visits, and at any time up to 52 weeks will be summarized.
- TUG time (secs) and percent change from baseline will also be summarized by metastatic/non-metastatic CRPC status, pain (yes, no pain), and opioid use (yes, no opioid use).
- At each assessment, status of TUG time will be summarized as the categories of improved, stable or worsened.
- Time to worsening in TUG time will be defined as time from randomization (or time from first dose for participants in the lead-in phase) to the first date a participant had a worsening. Time to worsening in TUG time will be summarized using Kaplan-Meier methodology, and a comparison between the two arms in the randomization phase will be made using a two-sided, stratified log-rank test, stratified by Age (<75, ≥75). The hazard ratio as well as its 95% CI will be presented using a stratified Cox regression model. An unstratified analysis will also be performed. The Kaplan-Meier plots will be provided for both stratified and unstratified analyses.
- Similar to the primary endpoint, the proportion of participants with a decline of at least 1 point in SPPB total score at 12 and 24 week study visits and at any time up to 24 and 52 weeks will be summarized. SPPB

will be analyzed by age (<75, ≥75), metastatic state (nmCRPC, mCRPC), Pain (yes, no pain), opioid use (yes, no opioid use).

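### At the 24-week lead-in cut, the crude 52-week TUG and SPPB worsening proportions are biased low whenever new worsening appears at Week 52

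*Protocol*

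**What the plan says.** Protocol 4.1 lists what is evaluated at the end of the lead-in phase. For TUG it is the proportion with "worsening in TUG time at week 12 and 24 and during the 24-week and 52-week period from baseline"; for SPPB, the proportion with "worsening in SPPB total score at week 12 and 24 and during the 24-week and 52-week period from baseline". The third item stops at 24 weeks: "decline in cognitive function during the 24-week period from baseline, as assessed by HVLT-R and TMT".

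The same section sets the lead-in primary analysis "when the last participant in the lead-in phase has been on the study for at least 24 weeks". SAP 5.4 agrees: it "will occur when the last participant has been on the study for at least 24 weeks". Both exempt participants who were lost, withdrew or died. Protocol 4.1 adds that, once feasibility has been judged, "the time point and time frame of evaluation of the endpoint for this part of the study will be chosen"; selection of the endpoint itself and a fresh look at the number of participants come at the same stage. SAP 3.1 repeats this.

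The schedule for the lead-in phase (Protocol Table 1–1, SAP Table 8–1) has TUG and SPPB at baseline and at Weeks 12, 24 and 52, with neither at Week 38.

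SAP 5.5.2 reports TUG worsening at the Week 12 and Week 24 visits "and at any time up to 52 weeks will be summarized", and SPPB worsening at any time up to 24 and 52 weeks. SAP 5.1 applies every analysis to both phases unless stated otherwise. SAP Table 3 admits anyone with a baseline and one later assessment. SAP 4.2 does not impute the primary TUG endpoint, apart from a sensitivity analysis that counts missing TUG as worsened. SAP 5.5.2 also defines a Kaplan-Meier time to TUG worsening, measured from first dose in the lead-in.

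**The concern.** A 52-week proportion is requested at a cut that guarantees only 24 weeks of follow-up. With no test between Weeks 24 and 52, the 52-week proportion can exceed the 24-week one only through the Week 52 visit. A participant who has not reached that visit adds to the denominator but cannot add a late event to the numerator. The plan has no rule for such participants.

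At stake is the comparison that the evaluation is meant to support. If the steering committee compares 24-week and 52-week worsening to choose a time frame, the 52-week figure will look closer to the 24-week figure than it is. If a 52-week endpoint were then chosen, the sample size would be reassessed from too low a rate.

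**Working it through.** **The plan's own figures reproduce.** For 20% versus 40%, one-sided alpha 10% and 85% power, with unpooled variance:

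n per arm = (1.2816 + 1.0364)² × (0.20×0.80 + 0.40×0.60) / 0.20² = 5.373 × 0.40 / 0.04 = 53.7, so 54. Two arms give 108, and 108 / 0.9 = 120, as stated in Protocol 9.2. The Table 9–1 limits also reproduce as exact binomial intervals for n = 30 (for example 6/30: 7.71 to 38.57). Neither is in dispute.

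**Inputs for the bias.**
- From the documents: about 30 lead-in participants ("Approximately 30 participants will receive study intervention in the lead-in phase of the study"), a cut 24 weeks after the last entry, and 20% worsening on darolutamide at 24 weeks (Protocol 9.2), used here as p24, the proportion worsened by 24 weeks.
- Assumed, because the documents do not give them: uniform accrual over A weeks, and the true proportion worsened by 52 weeks, p52.

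**Who can have a Week 52 test.** At the cut, follow-up runs evenly from 24 to 24 + A weeks. The share with at least 52 weeks is

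f = max(0, (A − 28) / A).

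It is zero when A is 28 weeks or less (about 27 if the 7-day early window is used). For A = 52, f = 24/52 = 0.462.

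**Expected crude 52-week proportion.** Participants past Week 52 contribute p52 and the rest contribute p24:

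crude = p24 + f × (p52 − p24), so bias = −(1 − f) × (p52 − p24).

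For A = 52 and p52 = 30%: 20 + 0.462 × 10 = 24.6%, a bias of −5.4 points.

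| Accrual A (weeks) | f | Expected of 30 past Week 52 | Crude figure if p52 = 30% | Bias, p52 = 25% | Bias, p52 = 30% | Bias, p52 = 38.3% |
|---|---|---|---|---|---|---|
| 28 or less | 0 | 0 | 20.0% | −5.0 | −10.0 | −18.3 |
| 36 | 0.222 | 6.7 | 22.2% | −3.9 | −7.8 | −14.3 |
| 52 | 0.462 | 13.8 | 24.6% | −2.7 | −5.4 | −9.9 |
| 78 | 0.641 | 19.2 | 26.4% | −1.8 | −3.6 | −6.6 |
| 104 | 0.731 | 21.9 | 27.3% | −1.3 | −2.7 | −4.9 |

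The 38.3% column is a constant hazard from 20% at 24 weeks: 1 − 0.8^(52/24) = 0.383.

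**The sensitivity analysis does not repair this.** If missing-as-worsened were extended to participants not yet at Week 52, the expected figure would be f × p52 + (1 − f). With p52 = 30% that is 100% for accrual of 28 weeks or less, 67.7% for 52 weeks and 48.8% for 104 weeks, so it errs the other way.

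**Effect on sample size, only if a 52-week frame were chosen.** Keep a 20-point difference and the other design values. A darolutamide rate of 30% (versus 50%) needs 5.373 × (0.21 + 0.25) / 0.04 = 61.8, so 62 per arm, and 124 / 0.9 = 137.8, so 138. A reported 20% in place of a true 30% would leave the total at 120.

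**The case against.** Several points on the other side have weight.

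- A reader might infer that the plan has no method that handles incomplete follow-up. That is not so for TUG: Protocol 9.4.2 and SAP 5.5.2 define a Kaplan-Meier time to worsening that covers lead-in participants. What remains is that the lead-in output index in SAP 9.0 lists no such table, and no time-to-event analysis is planned for SPPB.
- The cut is at least 24 weeks, and Protocol 4.1 allows extra lead-in participants, so it may fall later than assumed here. A later cut would shrink the bias, but nothing requires one.
- The end of the lead-in phase is not expressly equated with the 24-week primary evaluation. That is still the natural reading, because the randomized phase starts after that evaluation and its results determine the design.
- No numerical rule ties the 52-week proportion to the decision. The committee also sees Week 12, Week 24 and by-24-week figures, and a single-arm rate cannot show which time frame better separates the arms. This stands: distortion of the decision is possible but not demonstrated.
- With 30 participants, the exact intervals in Table 9–1 are 30.85 points wide at 20% and 36.74 at 40%, wider than any bias shown above. That is fair for a single rate. The comparison of 24 with 52 weeks, however, is made in the same people, and with short accrual the two figures are identical by construction.

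**Conclusion.** The point holds. Following the stated rules at a cut 24 weeks after the last entry gives a 52-week proportion that is too low whenever new worsening appears at Week 52. The direction follows from the text. The size does not, because accrual time and the 52-week rate are not given. With uniform accrual, 20% by 24 weeks and 30% by 52 weeks, the bias is −10 points for accrual of 28 weeks or less, −5.4 for 52 weeks and −2.7 for 104 weeks. Across the 52-week rates tried it ranges from −1.3 to −18.3.

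Stronger readings are not supported. The documents do not show that most participants will lack a Week 52 test, nor that the bias has any particular size. The planned 120 is not affected as it stands, since it rests on worsening at 24 weeks. Nor are lead-in data at Week 52 invalid: the schedule collects them, and the crude proportion is free of this bias once every participant has reached Week 52. The remedy is a correction of wording and outputs.

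**What to change.** 1. In Protocol 4.1 and SAP 5.5.2, limit the TUG and SPPB proportions in the 24-week lead-in evaluation to Week 12, Week 24 and by 24 weeks. This matches the 24-week limit on cognition in the same protocol list and the Week 12 and 24 limit on lead-in accelerometry in SAP 5.5.2.
2. If a 52-week figure is to inform the choice of time frame, use the Kaplan-Meier time to worsening with numbers at risk. Add the TUG table to the lead-in output index in SAP 9.0, add an SPPB equivalent, and state that participants without an event are censored at their last assessment. If nobody has reached Week 52 there is no 52-week estimate, and the output should say so. Alternatively, restrict the figure to participants enrolled at least 52 weeks before the cut and give their number.
3. Report the crude 52-week lead-in proportion only when every lead-in participant has reached Week 52 or discontinued.

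The cost is a few lines of text and at most two added outputs. No new data collection, visits or participants are needed.
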